## **ii. Intervention**

In order to reduce HIV risk in this study, all study participants will be screened for Chlamydia, gonorrhea (urogenital/anal CT, GC), syphilis and HIV infection and referred to PrEP care (if indicated) at all time points (see above).

The TLC Intervention follows a patient-centered case management and service delivery model and is delivered through a one day per week drop-in “one-stop-shop” milieu (“TransSafe”) and through on-going interactions with TLC staff, i.e., to provide referral and linkage to housing, employment, legal and medical services. Participants enter the TLC program through direct referral or through drop-in to TransSafe. Basic services needs are assessed upon entry into the TLC program through a brief intake with a staff member (to identify areas of service need/interest) and linkage to services (housing, employment, legal, medical) as needed, which are delivered over the entire 8-month enrollment period. TransSafe provides a social and service milieu in which participants may access services in a barrier-free and affirming environment. Participation in the TLC intervention may include referrals to services known as “TransWorks,” “TransHousing,” “TransLegal,” and “TransHealth”

The TransWorks Employment Program offers job readiness workshops, resume assistance, computer access, job search skill development, career counseling, and mentorship. In the TransHousing program, participants are referred to a Housing Specialist to identify tailored housing services and help to obtain documentation needed for supportive housing programs. The TransLegal program includes assistance with name change and gender marker change on identifying documents, record expungement and sealing, representation in employment and housing discrimination, representation in seeking public benefits, and misdemeanor defense. If the participant’s legal concerns fall outside of the scope of the TransLegal program, they are referred to alternative legal counsel. In the TransHealth program, TLC contracts with Heartland Health Outreach (HHO) to provide Medical Services on-site at the TransSafe drop-in program. For participants with a medical complaint, an HHO nurse practitioner meets with each individual and focuses on the presenting complaint; the medical provider also conducts a general health assessment, including sexual health risk assessment and need for cross-sex hormones and HIV prevention and treatment services. The provider makes referrals for any necessary continuing care, including PrEP initiation and care or HIV treatment services.

During COVID-19 restrictions, TLC services, including TransSafe, “TransWorks,” “TransHousing,” “TransLegal,” and “TransHealth” are offered in virtual mode, via telephone, web-based telehealth and teleconference, as well as email communication.

All study staff will receive training on human subjects’ protection, interviewing and data collection, and data handling prior to beginning engaged research activities. Study staff will be trained to remain neutral and professional in their interactions with participants and to encourage honest responses to the study questionnaire.

## **d. Data handling and Analysis**

Paper files include: 1) locator information, 2) informed consent, 3) intervention attendance records). The first two types of paper files have identifying information and are not considered study data. Consents are stored in a locked cabinet away from workstations and are only accessed in the event of a study visit, consent amendment, or an audit. Locator files are kept in a locked cabinet in the research area, separate

from data files, and are updated monthly and at each research visit. Case report forms are coded using a participant identification number (PID); intervention attendance records contain identifying information to increase data quality (de-identified attendance records would be difficult to accurately maintain) and stored in locked hard copy file cabinets or in password protected electronic files on a secure server. Only study staff will have access to paper file.

Computer files consist of the visit tracking data base, survey data files, case report forms (CRFs, i.e. for HIV/STI testing results and PrEP care) and audio recordings and transcriptions. In addition, during the COVID-19 pandemic, e-consent forms will be deployed and stored in REDCap, if a participant chooses to enroll remotely. Audio recordings are captured either on password protected audio recorders or through the audio recording feature of web conferencing platforms at Northwestern University (Zoom, Webex). Audio files contain no identifiers and are removed and deleted from audio recorders or web conferencing platforms and transferred immediately to secure study folders. Computer access is password protected. Data files are maintained in de-identified format and stored in password-protected files on secure servers. Tracking files (i.e., linking database) are maintained in a highly secure scheduling and monitoring database, REDCap, at Northwestern University. This database is used to schedule and track study visits and accessible only to study staff; it is completely password protected.

Survey data are captured in web-based format via Qualtrics software (in-person visits and for remote survey questionnaire), which uses Transport Layer Security (TLS) Encryption for all transmitted data; all data collected via Qualtrics is done only by ID number and not by name. Data files are exported from Qualtrics and imported into SPSS database for storage and analysis on a secure server at Lurie Children's. Only the study investigators and data manager have access to these data.

All biological specimens will be labeled with coded identifiers for processing to maintain confidentiality. Biological specimens (urine, anal swabs, blood) for HIV/STI testing will be coded and transferred by local courier for processing in external laboratories used commonly in the testing programs at Lurie Children's, Chicago House, and HHO. Hair samples for assessment of tenofovir disoproxil fumarate level (aka PrEP) will be coded and transferred to the Hair Analysis Lab at University of California San Francisco (UCSF) via mail courier service. All research staff will be trained for collection of hair samples by [name] with guidance from the Hair Analysis Lab at UCSF. DBS samples will be shipped via mail courier service to University of Colorado for analysis. Staff at HHO and/or Lurie Children's will be trained for collection and storage of DBS by [name]. HIV/STI testing will be completed by clinical staff of HHO or staff of Chicago House. Biological specimens collected under this protocol will be used for the purposes outlined herein and not for future research.

Coded and encrypted electronic data files collected at Chicago House, including program attendance records, HIV/STI screening results, and PrEP medical visit information will be transferred from Chicago House to Lurie Children's and from Lurie Children's (in a comprehensive database: survey, biomarker results, attendance records) to University of Chicago via REDCap ("send it" feature) for data analysis.

All identifying information will be destroyed as soon as possible at the end of study and no longer than three years from the closure of the study protocol with the Lurie Children's IRB.

Semi-structured interview data will be collected in a de-identified format, i.e., data will not be linked to individual names or identifiers. The audio-recorder and audio-recordings will be password-protected to protect against breach of confidentiality. Audio-recordings will be transcribed verbatim, with the exception that any inadvertent disclosure of names or other identifying information will be coded or excluded. Transcripts are entered into Dedoose qualitative analysis software for storage and analysis. Computer data files are maintained by ID number only, and are password protected and encrypted for transfer between study sites. Audio files will be destroyed as soon as possible after transcripts are

verified and no later than three years from the closure of the study protocol with the Lurie Children's IRB.

Data quality will be monitored regularly by the Lurie Children's PI and data manager. This will include review of study files and data for accuracy (Quality Assurance), reconciliation of any file and data problems as soon as possible, and cleaning of study data and creation of a codebook prior to analysis.

Only study investigators and the study data manager will have access to survey and interview data. Public access to the data will be provided at the completion of the study and after the dissemination of the main outcome findings. The study data sharing and use agreement describes in detail how data access will be provided and provisions for protection of privacy, confidentiality, security, intellectual property, or other rights (see Data Use Agreement, Appendix h).

Analyses will be conducted with SAS software (SAS Institute, Cary, NC). To determine the pre-post efficacy of the TLC intervention, we will assess the change in number of condomless anal sex acts from baseline to 4 and 8 months using paired t-tests or Wilcoxon signed rank tests for continuous outcomes, and McNemar's test for paired proportions for categorical outcomes. To maximize power, extensions of generalized linear models (GLMs) will be used to assess the combined effect of the intervention on condomless anal sex at 4 and 8-month follow-up. GLMs can accommodate dependent variables with normal, binary, Poisson, and negative binomial distributions and can be adapted to incorporate random and fixed effects (generalized linear mixed models; GLMMs) to account for within-subject correlation among repeated measures over time. Multivariable GLMMs will be used to assess frequency of condomless anal sex not protected by PrEP at 4- and 8-months post baseline, with an indicator for time as the primary explanatory variable. Models will also include the baseline value of the outcome, and covariates (e.g., age, race) that will be selected based on a priori hypotheses and empirical or theoretical importance. In the original analytic plan we proposed to treat time as discrete, assuming all visits occurred at 4 and 8 months within a margin of error. To account for differences in time between baseline and follow-up visits due to COVID-19 related changes in the recruitment protocol (i.e., extension of 4 and/or 8 month windows), we will conduct additional supplemental analyses to account for variability in person-time contribution among participants. We will calculate the exact time in days between baseline and subsequent visits as a continuous variable, and pre-post analyses will control for the time between measurements. For evaluation of the effect of intervention dose on rates of condomless anal sex over time, we will estimate relative rate ratios by specifying log-time as an offset variable in generalized linear models to account for varying person-time contributions. We will also include an indicator for whether stay at home orders were in place at the time of the assessment to control for behavioral changes that may have resulted from COVID-19 related policies. The analytic approach and interpretation of intervention effect estimates will otherwise be analogous to those described in the original proposal. Potential confounding and effect modification by sociodemographic characteristics and other factors will be examined in exploratory analysis and will be included in multivariable models as appropriate. All models will account for correlation among repeated measures on individuals over time. Inclusion of random effects for intercept and trend over time will be explored to assess subject-specific variability at baseline and in terms of trajectories over time.

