### **c. Study Design**

This study will take place in Chicago, Illinois at three sites with many years of supporting HIV prevention research: Chicago House and Social Service Agency (Chicago House), Ann & Robert H. Lurie Children’s Hospital of Chicago (Lurie Children’s) and University of Chicago (U of C). Study visits will take place at Chicago House and Lurie Children’s or, due to the COVID-19 pandemic, may occur virtually via teleconference or telephone; intervention delivery will occur at Chicago House or virtually via teleconference or telephone. Primary data analysis of de-identified data will take place at U of C and Lurie Children’s.

The specific aims of the study are as follows:

1. To determine the pre-post efficacy of the TLC intervention in a single arm trial on the primary outcome: number of condomless anal sex acts without protection by PrEP in the last month among 150 sexually active, HIV-uninfected TW (ages 17 and older), with assessments at baseline, 4 and 8 months.
  - a. To assess the dose response relationship by intervention exposure (i.e., the proportion of intervention components received/expressed need) as well as exposure to specific components (i.e., employment, housing, legal, and health) on reductions in the primary outcome.
  - b. To assess mediation of intervention effects on protective processes (gender affirmation, collective self-esteem, social support) theorized to increase with intervention exposure;
2. To examine the implementation experiences of TLC intervention participants and staff through semi-structured interviews with 20 TLC participants and 10 TLC and Chicago House staff members involved in delivery of services through the TLC intervention.
3. Exploratory Aims:

- a. To describe the trajectory of PrEP indication, uptake, retention and adherence in the community-based sample over an 8-month follow-up period and evaluate the impact of the TLC intervention on the PrEP continuum of care.
- b. To explore whether reductions in HIV risk are associated with epidemiologically-linked moderators including age and race/ethnicity.

Primary Hypotheses: We hypothesize that participants in the TLC intervention will demonstrate a reduction in number of condomless anal sex acts not protected by PrEP pre-post intervention.

Primary Outcome: The primary outcome of interest is the number of condomless anal sex acts without protection by pre-exposure prophylaxis (PrEP) reported in the previous month.

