### III. PROCEDURES/METHODS

#### a. Design

This study will use a pre-post design to compare pre-intervention levels of HIV risk to those at 4 and 8-months post baseline. Participants will be recruited from community-based locations, including venues and public places where TW socialize and congregate. 150 participants will be recruited over an 18-month enrollment period (5-6 per month) and then followed for a total of 8 months with follow-up data collected at 4 and 8-month visits. Additionally, semi-structured interviews will be conducted with TLC intervention participants and staff to describe implementation experiences and to identify areas for improvement of the intervention.

All of the study procedures are being done for research purposes.

Study Timeline: Participants will be enrolled over an 18-month rolling enrollment period and then followed for 8 months. The entire study will be conducted over a 4-year period. In Year 1, we will develop and submit the IRB protocol for approval to both the local Lurie Children's IRB and the CDC Project Determination, and will seek other reviews and approvals as needed and as requested by the CDC. We will also refine assessment instruments in consultation with the CDC. In Year 2, we will begin enrollment, implement the TLC intervention, and begin to conduct the qualitative interviews (i.e., timed to coincide with 8-month study visits). Enrollment for the trial will end in Year 3; follow-up visits and interviews will be completed in Years 2-4. In Year 4, we will complete remaining follow-up assessments, conduct final data analyses and complete translation planning and undertake dissemination efforts.

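### The regression model is written so that its time coefficient compares month 8 with month 4, not follow-up with baseline, and so cannot give the combined pre-post effect it is meant for

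*Protocol*

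**What the plan says.** The question is a pre-post one throughout. Aim 1 (Protocol, II.c Study Design) reads "To determine the pre-post efficacy of the TLC intervention in a single arm trial on the primary outcome", and the primary hypothesis is that participants "will demonstrate a reduction in number of condomless anal sex acts not protected by PrEP pre-post intervention". Section III.a Design describes a "pre-post design to compare pre-intervention levels of HIV risk to those at 4 and 8-months post baseline".

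Section III.d Data Handling and Analysis then gives two layers of analysis:

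- Paired tests: "we will assess the change in number of condomless anal sex acts from baseline to 4 and 8 months using paired t-tests", with Wilcoxon signed rank as the alternative and McNemar's test for categorical outcomes.
- Regression models, added to gain power, which "will be used to assess the combined effect of the intervention on condomless anal sex at 4 and 8-month follow-up". Their form is: "Multivariable GLMMs will be used to assess frequency of condomless anal sex not protected by PrEP at 4- and 8-months post baseline". The term of main interest in these models is a time indicator. The next sentence adds: "Models will also include the baseline value of the outcome", together with covariates such as age and race.

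The same section adds control for the exact time between visits and an indicator for stay-at-home orders. It also says that random intercepts and trends will be explored to describe variation between participants at baseline and over time. It does not say that baseline is an outcome row, or that the time indicator means post versus baseline.

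**The concern.** Adjusting for the baseline value is routine when randomised arms are compared, because the effect is then carried by the arm coefficient. Here there is one arm. Once baseline moves to the right-hand side, only months 4 and 8 remain as outcomes, and time can only separate those two visits.

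Two results are at stake. The first is the combined effect over both follow-ups, which the protocol assigns to this model. The second is the adjusted pre-post effect. Paired tests take no covariates, so age, race, time between visits and stay-at-home orders can be handled only in a regression. The last of these matters most: without a control group, a fall in sexual activity under COVID-19 restrictions could look like an intervention effect. A reader could also meet a significant paired test beside a null coefficient for the model's primary explanatory variable, with nothing to explain that the two answer different questions.

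**Working it through.** **1. The plan's own figure.** The Sampling section (III.b.ii) gives 150 enrolled and 20% attrition: 150 × 0.80 = 120. For a paired t-test with d = 0.32 on the SD of the differences, the noncentrality is 0.32 × √120 = 3.51, giving 93.5% power (two-sided 0.05, assumed, since the protocol states no alpha). For McNemar's test of 40% versus 25%, power is 78.3% at a within-person correlation of 0.2 and 83.3% at 0.3. The stated power of over 80% therefore holds for the proportions from a correlation of about 0.25. This power belongs to a baseline-versus-follow-up contrast and does not carry over to a month-8-versus-month-4 contrast.

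**2. The model as written.** With Y the count, t = 4 or 8, X the covariates and b the participant effect:

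log E(Y at t) = β0 + β1·[t = 8] + γ·g(baseline Y) + δ·X + b

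So exp(β1) = (mean at 8)/(mean at 4), given baseline. The baseline mean is not modelled, and no coefficient equals follow-up divided by baseline. This follows from the structure and needs no simulation.

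**3. Size.** Assumed inputs: n = 120, Poisson counts, log-normal participant effect with SD 1 on the log scale, baseline mean 4, 400 runs per scenario. A Poisson GEE with exchangeable correlation stood in for the GLMM, and the baseline covariate was log(baseline + 1). Each cell gives the estimated rate ratio and, in brackets, the share of runs rejecting at 0.05.

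| True means at 0, 4, 8 months | True 8 vs 4 | Time ratio, model as written | True pooled follow-up vs baseline | Three-visit model |
|---|---|---|---|---|
| 4, 2, 2 | 2/2 = 1.00 | 0.995 (4.8%) | 2/4 = 0.50 | 0.501 (100%) |
| 4, 4, 4 | 4/4 = 1.00 | 1.002 (5.0%) | 4/4 = 1.00 | 1.006 (6.8%) |
| 4, 2, 4 | 4/2 = 2.00 | 2.004 (100%) | 3/4 = 0.75 | 0.753 (100%) |
| 4, 4, 2 | 2/4 = 0.50 | 0.503 (100%) | 3/4 = 0.75 | 0.750 (99.3%) |

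The first two rows cannot be told apart by the model as written: a sustained halving looks like no change. In the third, a benefit lost by month 8 appears as a doubling, although acts are only back at baseline.

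**4. The other reading: baseline as outcome row and covariate.** In the Poisson GEE above this gave 0.501, the same as without the covariate. Mixed models were run with n = 120, baseline mean 3, dispersion 1, random-intercept SD 1 and a true ratio of 0.60:

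- Poisson mixed model: 0.595 with the baseline covariate and 0.595 without (25 runs). With complete data, a covariate that is constant within a participant cancels from the visit contrast.
- Negative binomial mixed model with the covariate: 0.84 (25 runs), 0.86 (60 runs, 15% rejection) and 0.88 (80 runs, 19%); 0.75 (60 runs, 43%) with baseline on its raw scale.
- Negative binomial mixed model without the covariate: 0.59 (60 runs, 93%) and 0.60 (80 runs, 85%).
- Negative binomial mixed model with the covariate, but counts generated without the extra dispersion: 0.592 (25 runs).

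The bias toward no change thus appears when a negative binomial mixed model meets overdispersed counts, and not otherwise in these checks. The run numbers are small, so the direction is firmer than the second decimal.

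**The case against.** The strongest reply has four parts.

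- *The model is not the primary analysis.* This stands. The protocol attaches the word primary to the explanatory variable, not to the model; it assigns pre-post efficacy to the paired tests and bases the power on them. A reader might infer that Aim 1 has no valid test, or that a sustained reduction would be reported as no effect. Neither follows, because the paired tests would report it.
- *Other sentences suggest that baseline is an outcome row.* The stated purpose of a combined effect, the design statement and the mention of variation at baseline all point that way, and person-specific trends make little sense with two rows per person. This is a fair reading of intent. It does not repair the text, which names the 4- and 8-month values as the outcome and would then place baseline on both sides of the equation.
- *On that reading there is no general bias.* This also stands. A reader might infer that any count mixed model with baseline on both sides is distorted. The Poisson results show otherwise, and the protocol lists normal, binary, Poisson and negative binomial distributions without choosing one.
- *Row structure and contrasts belong in the SAP.* Ordinarily they do. Here the protocol already fixes the outcome visits, the main term and the baseline covariate, and together these give the wrong contrast. A predicted follow-up mean could be set against the observed baseline mean, but the protocol names no such step.

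**Conclusion.** The point holds for the regression model and not for the plan as a whole. As written, the time coefficient estimates month 8 versus month 4, and the combined and covariate-adjusted baseline-to-follow-up effects are not estimated. That rests only on the model's structure. The sizes rest on assumed means, variances and distributions: a time ratio of about 1.0 when the true pre-post ratio is 0.50, and about 2.0 when an early benefit is lost. If baseline is meant to be an outcome row as well, the baseline covariate is redundant in a Poisson mixed model or GEE with complete data. In a negative binomial mixed model with overdispersed counts it can pull the effect toward no change (a true 0.60 estimated at 0.75 to 0.88). Aim 1 keeps a valid unadjusted paired test at each visit. The wording should be corrected before analysis.

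**What to change.** In section III.d, and in the SAP if there is one:

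- Name all three visits (baseline, 4 and 8 months) as repeated responses in the mixed model, with visit indicators and baseline as the reference visit.
- Make the follow-up-versus-baseline rate ratios the model's main contrast: 4 months, 8 months and their average. State the scale of the average, since an equal-weight average on the log scale differs from a ratio of pooled means (for visit ratios of 0.50 and 1.00, √0.50 = 0.71 against 0.75).
- Delete the baseline value of the outcome from this model's covariates. Keep age, race, time between visits and the stay-at-home indicator.
- Leave the count distribution to the data or the SAP.

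The cost is a few sentences of wording. No new data, visits or participants are needed, and the paired tests stay as they are.

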### **i. Variables**

*Primary outcome:* The primary outcome, condomless anal sex acts not protected by PrEP adherence (defined as anal sex acts without a condom in the prior month without use of PrEP at protective levels) will be analyzed as a composite variable of condomless anal sex acts that confer risk in the prior month, adjusting condomless acts to “0” for those participants with protective levels of PrEP adherence verified by biomarker (i.e., hair analysis, see below). We will use the AIDS-Risk Behavior Assessment (ARBA; revised for transgender women) for measurement of sexual risk. The ARBA is a computerized self-interview designed to assess self-reported sexual behaviors. Self-reported PrEP adherence will be measured using time-line follow-back (TLFB) for the 1-month recall period. Objective verification via hair samples will only be completed for those individuals who report levels of adherence consistent with protection over the entire recall period (i.e., 4 doses/week for PrEP). We will collect hair samples (100 strands) for analysis of uptake/adherence to PrEP (tenofovir disoproxil fumarate). Hair analysis will be completed at the University of California (UCSF) Hair Analysis Lab. Among participants from whom a hair sample is not feasible, either due to short hair or hair extensions, for example, a blood sample will be collected via a dry blood spot (DBS), for analysis of PrEP level. The DBS will be collected by venipuncture (4mL of blood or approximately one teaspoon). DBS processing and analysis will be performed by University of Colorado. During the COVID-19 pandemic, no hair or DBS samples will be collected at any time point.

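### The dose model's log-time offset does not fit an outcome counted over a fixed one-month recall, and can bias the dose effect where dose rises with elapsed time

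*Protocol*

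**What the plan says.** Protocol section II.c (Study Design) defines the primary outcome as the "number of condomless anal sex acts without protection by pre-exposure prophylaxis (PrEP) reported in the previous month". Section III.c.i (Variables) repeats the window: "defined as anal sex acts without a condom in the prior month without use of PrEP at protective levels". The PrEP part of the composite uses the same window: "Self-reported PrEP adherence will be measured using time-line follow-back (TLFB) for the 1-month recall period". Section III.a (Design) has "follow-up data collected at 4 and 8-month visits".

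Section III.d (Data Handling and Analysis) then adds supplemental time adjustments because COVID-19 led to an "extension of 4 and/or 8 month windows". It states: "We will calculate the exact time in days between baseline and subsequent visits as a continuous variable". Pre-post analyses are to control for that time. For the effect of dose, however, "we will estimate relative rate ratios by specifying log-time as an offset variable in generalized linear models to account for varying person-time contributions".

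Aim 1a in section II.c asks whether exposure, taken as the share of needed components received, is related to reductions in the primary outcome. Section III.c.ii (Intervention) has services delivered throughout the 8 months.

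**The concern.** A log-time offset turns a count into a rate per unit of time. That is right when events are counted over the whole of that time. Here every assessment counts acts over one month, whether it takes place at 4 months, at 8 months or late. Elapsed time since baseline is not the time at risk for the count, so the model divides a one-month count by four, eight or more months.

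At stake is the answer to Aim 1a. The offset lowers the modelled rate as follow-up lengthens. If exposure also grows with follow-up, the two move together and the model can show a protective dose effect that is not there. Late visits, which the adjustment is meant to handle, are credited with lower risk simply for being late.

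**Working it through.** The protocol gives no figure for the dose analysis, so there is none to reproduce.

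**Which time is meant.** The dose sentence does not define log-time. The recall window is the same for everyone, so an offset based on it would be a constant and could not account for anything that varies. Days since baseline, defined shortly before, is the only candidate that varies. This is an inference, but the natural one.

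**What the offset does.** With log E[Y] = log(t) + Xβ, the model describes E[Y]/t. If behaviour is unchanged, E[Y] is the same at both visits and the fitted ratio is t4/t8.

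- 3 acts per month at both visits: 3/4 = 0.75 at 4 months and 3/8 = 0.375 at 8 months, ratio 0.375/0.75 = 0.50.
- A 4-month visit held at 6 months: scaled by 4/6 = 0.67.
- An 8-month visit held at 12 months: scaled by 8/12 = 0.67.

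With a constant one-month offset the 8- versus 4-month ratio is 1.00.

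**What this does to the dose coefficient.** Under no true effect, log E[Y] is constant, so the model must fit −log(t) with its covariates. The dose coefficient is then roughly minus the slope of log(t) on dose. It is zero if dose is unrelated to elapsed time and negative (apparently protective) if dose rises with it. A visit term removes the 4-to-8-month part and leaves only the slope within visits.

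**Simulation under a true null.** From the protocol: 120 participants (the final sample in section III.b.ii, Sampling) and two follow-up visits. Assumed: negative binomial counts with mean 4 per month and participant effects; visits centred on days 122 and 243; visit spread with log-SD 0, 0.15 or 0.30; dose accruing with time, either as a running total or as a proportion that levels off. Each setting had 400 runs of a Poisson GEE with robust standard errors, tested at 5%. At the first visit, one SD either way is about 105 to 142 days for log-SD 0.15 (122 × e^±0.15) and about 90 to 165 days for 0.30.

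| Model | Visit spread (log-SD) | RR per SD of dose | False positives |
|---|---|---|---|
| Offset, no visit term | 0 | 0.83–0.84 | 43–46% |
| Offset, no visit term | 0.15 | 0.81–0.82 | 47–60% |
| Offset, no visit term | 0.30 | 0.75–0.76 | 65–79% |
| Offset, visit term | 0 | 0.99 | 7–10% |
| Offset, visit term | 0.15 | 0.96 | 7–9% |
| Offset, visit term | 0.30 | 0.87–0.88 | 25–27% |
| Constant offset, no visit term | 0.15 | 1.00 | 6–8% |
| Constant offset, visit term | 0.15 | 0.98–0.99 | 8% |
| Offset, dose unrelated to time | 0.15 | 1.00 | about 7% |

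Where a visit term is fitted with the elapsed-time offset, the halving moves into that term (8- versus 4-month ratio 0.50 to 0.55).

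**The case against.** A reader might infer that the offset is certain to create a false dose-response. The documents do not support that, for three reasons.

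- Dose is defined relative to expressed need, not as a running total. Accrual over 8 months of services is plausible, but it is not stated. If dose is unrelated to elapsed time, nothing happens to the dose coefficient. If people with delayed visits received a smaller share of what they needed, the bias within visits would run the other way.
- The outcome models in section III.d carry a time indicator, and the section says the approach otherwise follows the original proposal. The dose sentence does not repeat the indicator, but it may well be inherited. If so, most of the bias goes into the visit effect, and false positives stay close to the 6–8% seen without the offset unless visits are widely spread.
- The protocol gives neither visit spread nor dose accrual, so the simulated sizes rest on assumptions.

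A reader might also infer that the model fails at baseline, where elapsed time is zero and its logarithm undefined. Section III.d models the 4- and 8-month outcomes with the baseline value as a covariate. On that structure baseline is not an outcome row and the problem does not arise.

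Finally, these adjustments are introduced as supplemental and the offset is confined to the dose analysis. The pre-post analyses only control for elapsed time, so the primary test does not carry this error.

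All of this limits the consequence. None of it makes the offset right: at best another term in the model absorbs it.

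**Conclusion.** Wrong as written; it should be fixed. An elapsed-time offset does not match a count over a fixed one-month recall. The halving of the 8-month rate relative to the 4-month rate under unchanged behaviour (0.50), and the factor of 0.67 for a 4-month visit held at 6 months, follow from arithmetic once log-time is read as time since baseline.

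A spurious protective dose effect is possible, not certain. It needs dose to rise with elapsed time, and its size depends on whether a visit term is fitted and how far visits spread: large without a visit term, small with one and modest spread, and material again with one at a log-SD of 0.30. Those sizes hold only for the assumed inputs. The point concerns Aim 1a and not the primary pre-post comparison. It is not a detail left open for a statistical analysis plan, because the protocol itself specifies the offset.

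**What to change.** In section III.d, delete the log-time offset from the dose model, or define it as the log of the one-month recall window, which is the same for everyone. State that the dose model includes visit, and either days since baseline or deviation from the planned visit day, as covariates. This handles late visits in the way the section already does for the pre-post analyses. The cost is a change of wording in the protocol, and in the analysis plan if it repeats the sentence. No extra data are needed, since the visit dates are already used to compute elapsed days. The change should be made before the dose analysis is run.
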